## 5.2 Exclusion Criteria

A patient will not be eligible for this study if any of the following exclusion criteria are met:

- 5.2.1 Serious concomitant systemic disorder that would compromise the safety of the patient or compromise the patient's ability to complete the study, at the discretion of the investigator.
- 5.2.2 Patients may have received prior ADT in the neoadjuvant, adjuvant and/or salvage setting, but must be off therapy for at least 3 months and have a testosterone level  $>$  150 ng/dL.
- 5.2.3 Second primary malignancy except most situ carcinoma (e.g. adequately treated non-melanomatous carcinoma of the skin) or other malignancy completely resected with no recurrence.
- 5.2.4 Patients with type II diabetes currently already on metformin.
- 5.2.5 Patients taking aspirin for previously diagnosed cardiovascular disease.
- 5.2.6 Patients who received aspirin or metformin within the past 28 days.
- 5.2.7 Patients taking medications with known interactions with metformin or aspirin.
- 5.2.8 Patients taking warfarin or platelet inhibitors.
- 5.2.9 Patients requiring chronic use of NSAIDS.
- 5.2.10 Other concurrent experimental or investigational drugs.
- 5.2.11 Prior history of lactic acidosis or metabolic acidosis.
- 5.2.12 Patients with history of GI bleeding and peptic ulcer disease within the past 6 months.
- 5.2.13 Any unstable, serious co-existing medical conditions including but not limited to myocardial infarction, coronary bypass surgery, unstable angina, cardiac arrhythmias, clinically evident congestive heart failure, or cerebrovascular accident within 6 months prior to screening.

Prot [REDACTED]

Title: A Phase 2 Randomized Discontinuation Trial in Patients with Hormone-Dependent Rising Prostate-Specific Antigen Progression After Local Therapy for Prostate Cancer Evaluating the Synergy of Metformin Plus Aspirin (PRIMA Trial).

PI: [REDACTED]

### 5.3 Women and Minorities

Men from all racial/ethnic groups are eligible for this study if they meet the eligibility criteria. Women will not be eligible for this study as prostate cancer does not occur in women.

### 5.4 Children

Only patients 18 years of age or older will be enrolled on this study, since prostate cancer does not occur in children.

### 5.5 Study Enrollment Procedures

A copy of the institution's IRB-approved informed consent document and written justification [REDACTED]

[REDACTED] Research Services (OQRS) before any participating institution may enter patients. Consent forms proposed for use at a participating institution must be reviewed and approved by the OQRS Regulatory Affairs Manager and all documents must be received (i.e., IRB approved documentation, IRB approved consent form, See Section 15.2 for a complete list of regulatory items).

Participating institutions will register patients through the [REDACTED] Registration Desk telephone: [REDACTED]. Patient demographic information, the signed and dated study-specific eligibility checklist and completed signature page of the consent form and additional source documents if requested by OQRS must be sent to the registration desk. Once the OQRS Registration Desk verifies eligibility, a unique patient study number will be issued. The patient will not be identified by name. This is the point that the patient is considered on study.

**Patients must not start protocol treatment prior to registration.**

If a patient does not receive any protocol therapy, baseline data will be collected and submitted on the pre-study and follow-up electronic case report forms (eCRF) through Oncore®. The reason for not starting protocol therapy will be documented in the "follow-up eCRF". Case report form completion instructions and training will be provided to each participating institution prior to study activation at the participating institution.

## 6. Study Parameters

The following tests and evaluations will be performed according to the schedule below. Baseline (i.e., pre-study) evaluations must be performed within 4 weeks (+/- 3 days) after enrollment, and prior to therapy, unless otherwise indicated in one of the footnotes below in the table. The study drugs, correlative studies, and salicylate levels will be paid for by [REDACTED]

[REDACTED] will be billed to the subject's insurance company.

Protocol Version 8.0 12/01/2017

Title: A Phase 2 Randomized Discontinuation Trial in Patients with Hormone-Dependent Rising Prostate-Specific Antigen Progression After Local Therapy for Prostate Cancer Evaluating the Synergy of Metformin Plus Aspirin (PRIMA Trial).

PI: [REDACTED]

Evaluations	Pre-Study	On Treatment (every 4 weeks $\pm$ 3 days)	Randomization Day 1 of 1 st Cycle Post 4 Month Lead-In	Off Treatment (+30 days)	Follow Up 
Initial History & Physical 	X				
Interim History & Physical		X 		X	
Toxicity Assessment	X	X 		X	
ECOG Performance Status	X	X 		X	
Weight and Vitals	X	X		X	
CBC, differential, platelets	X 	X 		X	
Serum Chemistries 	X	X 		X	
Liver Enzymes 	X			X	
Radiographic Assessments 	X				
Correlative Studies 	X	X		X	
Compliance Assessment		X		X	
Salicylate levels 	X	X 			
Prostate-specific antigen (PSA) *	X 	X	X 	X	X
	
 
1. Within 4 weeks of enrollment. Second PSA will be obtained within a week of starting C1D1 (this PSA will establish a baseline to assess response and will not determine eligibility).
 
2. Includes: Electrolytes, Calcium, BUN, Creatinine, Glucose.
 
3. Includes: Total and Direct Bilirubin, AST/ALT, Alkaline Phosphatase, Albumin, Total Protein.
 
4. A bone scan and a CT or MRI abdomen/pelvis and chest x-ray (CXR) or chest CT scan, will have been performed within 12 weeks of treatment start. Radiographic assessments will be selected by the attending physician as clinically indicated.
 
5. See Section 11 for details of laboratory evaluations. These analysis are optional however, every effort should be made to collect samples for analysis.
 
6. Salicylate levels will be drawn at baseline and through Cycle 5. Salicylate levels will NOT be collected after Cycle 5. Salicylate levels drawn at C1D1 are acceptable as baseline Salicylate levels as long as they are drawn prior to drug administration.
 
7. All patients, including those who discontinue protocol therapy early, will be followed for response (or progression) with PSA every 12-16 weeks and for survival for 1 year from the date of registration.
 
8. PSA will be drawn within 1 week of 1st Cycle of Treatment.
 
9. The research nurse will call the patient 2 weeks after starting metformin to assess for GI toxicity.
 
10. The H&P, ECOG and labs do not need to be repeated on C1D1 if these were completed within the pre-study time point.
 
 
* PSA should preferably be collected at the same lab for all time-points to prevent PSA fluctuations between different labs.
				

Protocol [REDACTED]

Title: A Phase 2 Randomized Discontinuation Trial in Patients with Hormone-Dependent Rising Prostate-Specific Antigen Progression After Local Therapy for Prostate Cancer Evaluating the Synergy of Metformin Plus Aspirin (PRIMA Trial).

PI: [REDACTED]

## 7. Treatment Plan

### 7.1 General Considerations

Treatment will be administered on an outpatient basis. No investigational or commercial agents or therapies other than those described below may be administered with the intent to treat the patient's malignancy. Patients may discontinue therapy at any time for any reason.

### 7.2 Study Agent

Metformin treatment will be started at 500 mg twice daily, if no GI toxicity grade greater than 1 is noted after 2 weeks it will be increased to 500 mg with breakfast/1000 mg at bedtime, which is the target dose for the remainder of the study. If GI toxicity grade greater than 1 occurs during the first 4 weeks, the subject will be evaluated every 2 weeks until resolution of toxicity to grade less than or equal to 1 and, then, the metformin dose will be increased to the next dose level. Metformin will be taken with food in order to minimize gastrointestinal side effects.

Aspirin will be taken at a dose of 81 mg once daily. Aspirin must be taken with food.

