### 7.3 Dose Modifications or Escalations

#### 7.3.1 Toxicity

Any Grade 3 or 4 non-hematologic adverse event, or Grade  $\geq 2$  renal toxicity, thought to be drug-related will lead to cessation of medications. If any of these occur, the patient will be removed from the study.

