#### 7.3.2 Dose Reduction

Dose modification will not occur for any reason.

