## 10. Removal of Patients from Study/Off Study Criteria

In the absence of treatment delays due to adverse events, treatment may continue until one of the following criteria applies:

- a) Intercurrent illness that prevents further administration of treatment,
- b) Unacceptable adverse event(s),
- c) In the event of any drug-related life-threatening toxicity or laboratory abnormality the patient will be withdrawn from further treatment,
- d) Patient decides to withdraw from the study,
- e) Noncompliance with treatment plan,
- f) General or specific changes in the patient's condition that render the patient unacceptable for further treatment in the judgment of the investigator, or
- g) Protocol violation - any patient found to have entered this study in violation of the protocol might be discontinued from the study at the discretion of the Principal Investigator.
- h) PSA progression after at least 30 days of treatment (see Section 4.5).

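### For drug-related grade 3–4 GI toxicity in the first 4 weeks, 7.2 and 7.3.1 give opposite instructions, and 7.2's dose-increase step names no level for men already at the target dose

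*Combined protocol and SAP*

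**What the plan says.** Section 7.2 starts metformin at 500 mg twice daily. The planned step comes at two weeks: "if no GI toxicity grade greater than 1 is noted after 2 weeks it will be increased" to 500 mg with breakfast and 1000 mg at bedtime, "which is the target dose for the remainder of the study". A second rule follows in the same paragraph: "If GI toxicity grade greater than 1 occurs during the first 4 weeks", the man is evaluated every two weeks until the toxicity is grade 1 or lower, and "then, the metformin dose will be increased to the next dose level".

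Section 7.3.1 has its own trigger: "Any Grade 3 or 4 non-hematologic adverse event" (or renal toxicity of grade 2 or higher) that is thought to be drug-related. It requires cessation of the medications and adds: "If any of these occur, the patient will be removed from the study".

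Section 7.3.2, under the title Dose Reduction, says: "Dose modification will not occur for any reason".

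Sections 4.2, 4.3 and 4.4 repeat 500 mg plus 1000 mg per day as the continuing metformin dose. Section 12.1 gives the product dosing as 1000 mg twice daily.

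**The concern.** The titration rule and the stopping rule overlap in grade, in type of event and in time, and they point in opposite directions where they overlap. A site that follows 7.2 keeps the man under observation and then raises his dose. A site that follows 7.3.1 stops treatment and takes him off study. Both would be following the protocol.

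The titration rule also stays open for two weeks after the planned escalation. In that interval it tells the site to increase the dose of a man who is already at target, without naming a level.

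GI effects are the leading expected reactions to metformin (12.1, 17.2), and the study calendar in Section 6 schedules a nurse call at two weeks to look for them. The rules therefore bear on patient safety, on the feasibility and safety objective (1.2.1), and on which men stay in the run-in long enough to be considered for randomization. Section 3 allows network sites to take part, so different readings at different sites are possible.

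**Working it through.** There is no stated figure to reproduce. The check compares the triggers and actions of the rules and tracks the dose a man is on when each applies.

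**Doses**
- Starting dose (7.2): 500 + 500 = 1000 mg/day.
- Target dose (7.2, 4.2–4.4): 500 + 1000 = 1500 mg/day. The step is 500/1000 = 50%.
- Dose listed in 12.1: 1000 + 1000 = 2000 mg/day, which is 500 mg/day above the target.

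**Triggers**
- 7.2 GI rule: GI toxicity of grade 2, 3 or 4, any cause, weeks 0–4, at either dose.
- 7.3.1: grade 3 or 4 non-hematologic event, drug-related, any time, any dose. GI events are non-hematologic and are not excepted.
- Overlap: drug-related GI toxicity of grade 3–4 in weeks 0–4.

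**Time**
- The planned escalation is at week 2 and the GI rule ends at week 4. In weeks 2–4, a man escalated on schedule is at 1500 mg/day and still inside the 7.2 window.

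**What each rule says for GI toxicity in weeks 0–4**

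| Event | 7.2 | 7.3.1 | Result |
|---|---|---|---|
| Grade 2, starting dose | Evaluate, then 1000 to 1500 mg/day | Not triggered | No conflict between the two |
| Grade 2, at target (weeks 2–4) | Evaluate, then increase from 1500 mg/day to an unnamed level | Not triggered | Increase has no referent |
| Grade 3–4 drug-related, starting dose | Evaluate, then 1000 to 1500 mg/day | Stop and remove | Opposite instructions |
| Grade 3–4 drug-related, at target (weeks 2–4) | Evaluate, then increase to an unnamed level | Stop and remove | Opposite instructions, and no referent |
| Grade 3–4 judged unrelated | As for grade 2 at the same dose | Not triggered | As for grade 2 at the same dose |

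No section states which rule takes precedence in the third and fourth rows. There is no table of dose levels from which the unnamed level could be read.

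**Relation to 7.3.2.** Its sentence bars dose modification without exception, while 7.2 provides for a dose change. The title of 7.3.2 concerns reductions only, but its parent heading, 7.3, covers modifications and escalations together. The text therefore does not settle whether the 7.2 titration is an exception.

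**The case against.** The strongest reply is that the two rules can be read together: 7.2 governs titration and 7.3.1 governs stopping. Section 7.3.1 is categorical, Section 10 b) and c) also end treatment for unacceptable or life-threatening events, and a man who has been removed has no dose left to increase. This is a coherent reading, but the documents do not state it. Section 7.2 gives its own instruction for every grade above 1 and does not refer to 7.3.1. What stands of the reply is that the overlap is narrow: it excludes grade 2 events, events judged unrelated to drug, and everything after week 4.

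On the dose increase, a reader might infer that 7.2 orders a dose above target after toxicity at target, perhaps the figure in 12.1. The documents do not support that. Section 7.2 names no higher level, fixes the target for the rest of the study, and 4.2–4.4 repeat that dose. The sentence may have been meant only as a delayed step from the starting dose to target. What remains is an instruction without a referent for men already escalated, made less clear by the different dose in 12.1.

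A reader might also infer a gap for grade 2 GI toxicity after week 4, or while toxicity is unresolved, because Section 10 opens with "In the absence of treatment delays due to adverse events, treatment may continue until one of the following criteria applies" and Section 7 provides for no delay. The text does give an answer: 7.3.2 leaves the dose unchanged, and Section 10 b) and f) allow treatment to stop for unacceptable events or on the investigator's judgment. The reference to delays is a loose end, not a contradiction.

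Finally, titration takes place in the open-label run-in. It can change who is randomized, but it precedes randomization and so does not itself bias the comparison between arms.

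**Conclusion.** The plan is wrong as written on two limited points.

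1. For drug-related grade 3–4 GI toxicity in weeks 0–4, 7.2 and 7.3.1 give opposite instructions and no precedence is stated. On the starting dose, the difference is between a 50% increase in daily metformin and removal from the study.
2. For a man already at 1500 mg/day with GI toxicity above grade 1 in weeks 2–4, the instructed increase has no defined level and sits against the stated target.

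Both follow from the wording alone and rest on no assumed rate. It is tempting to apply a guessed rate of GI toxicity of grade 2 or higher to the 66 registered men. The documents give no such rate, and the result would include men with grade 2 events on the starting dose, for whom 7.2 and 7.3.1 do not conflict. The number affected therefore cannot be derived. Sample size and power are unaffected. The point should be corrected because it bears on safety and on who stays in the run-in.

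**What to change.** Reconcile 7.2, 7.3.1, 7.3.2 and 12.1, and carry any change into 4.2, which repeats the titration step without the GI rule:

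- State which CTCAE grades the 7.2 GI rule covers, so that it and 7.3.1 do not both apply to the same event.
- Replace the reference to a next dose level with a named level, and say whether the sentence applies only to men still on the starting dose.
- State whether the 7.2 titration is an exception to 7.3.2.
- Bring the metformin dosing in 12.1 and in 7.2 into agreement.

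Which clinical action and which dose apply in each case is for the sponsor to decide. The cost is a wording amendment with its usual approval and notice to sites. It adds no patients, visits or procedures.

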### Missed Doses

If patients vomit after taking medications, patients should be instructed not to retake the dose. Patients should take the next dose at the scheduled time.

If a scheduled dose is missed, patients should be instructed to take the dose as soon as remembered. If it is within 4 hours of their next dose they should be instructed to skip the dose and resume their usual dosing schedule. Patients should not double their dose to catch up missed doses.

### 7.3 Dose Modifications or Escalations

#### 7.3.1 Toxicity

Any Grade 3 or 4 non-hematologic adverse event, or Grade  $\geq 2$  renal toxicity, thought to be drug-related will lead to cessation of medications. If any of these occur, the patient will be removed from the study.

#### 7.3.2 Dose Reduction

Dose modification will not occur for any reason.

### 7.4 Concomitant Medications

Patients may take any type of FDA approved pharmacologic agents while enrolled on this clinical trial.

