### 7.5 Supportive Care Guidelines

Patients are allowed to receive full supportive care therapies concomitantly during the study. No other chemotherapy, immunotherapy, hormonal cancer therapy, radiation therapy, surgery for cancer, or experimental medications will be permitted while the patients are participating in

[REDACTED] J #: 081501

Title: A Phase 2 Randomized Discontinuation Trial in Patients with Hormone-Dependent Rising Prostate-Specific Antigen Progression After Local Therapy for Prostate Cancer Evaluating the Synergy of Metformin Plus Aspirin (PRIMA Trial).

PI: [REDACTED]

this study. It is not anticipated that patients will require significant supportive care. They may experience nausea and vomiting and the administration of antiemetic agents to control these symptoms would be acceptable.

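### Section 7.4 permits any FDA-approved drug on study, and no section carries the entry bars on aspirin, metformin, anticoagulants, NSAIDs and interacting drugs (5.2.4-5.2.9) past enrolment for non-cancer use

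*Combined protocol and SAP*

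**What the plan says.** Section 7.4 is a single sentence: "Patients may take any type of FDA approved pharmacologic agents while enrolled on this clinical trial". It applies to the whole time on study and has no exceptions.

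Two other sections limit treatment on study. Section 7.1 says: "No investigational or commercial agents or therapies other than those described below may be administered with the intent to treat" the malignancy. Section 7.5 says: "No other chemotherapy, immunotherapy, hormonal cancer therapy, radiation therapy, surgery for cancer, or experimental medications will be permitted". Both concern anticancer or experimental treatment.

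The drugs at issue appear in Section 5.2, whose opening sentence makes every item a test of eligibility. Items 5.2.4 and 5.2.5 exclude diabetic patients already on metformin and patients on aspirin for cardiovascular disease. Item 5.2.6 excludes "Patients who received aspirin or metformin within the past 28 days", 5.2.7 excludes users of interacting drugs, 5.2.8 excludes "Patients taking warfarin or platelet inhibitors" and 5.2.9 excludes "Patients requiring chronic use of NSAIDS".

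The control after randomisation is placebo metformin plus placebo aspirin (4.3). Section 17.2 names peptic ulcer disease and GI bleeding as aspirin risks.

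**The concern.** The protocol treats these drugs as serious enough to exclude a patient, with a 28-day look-back for the two study drugs, and then permits all of them once the patient is enrolled. Two things are at stake.

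**Comparison of arms.** Aspirin and metformin are ordinary commercial drugs. A placebo patient who starts either one for a non-cancer reason receives part of the tested regimen, which pulls the placebo progression rate towards the active rate. Because 7.4 permits it, this is not a deviation and nothing in the plan flags it.

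**Safety.** All patients take aspirin in the run-in, and some take it under blind afterwards. A clinician who adds warfarin or a platelet inhibitor after randomisation does not know whether aspirin is already on board, and the protocol gives no preset rule. This concern needs no assumption about how often it happens.

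**Working it through.** **1. Does any section close the gap?**

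- 7.1 and 7.5: anticancer or experimental treatment only. Aspirin for the heart or metformin for new diabetes is neither.
- 5.2.4-5.2.9: eligibility only.
- 7.3.1: drug-related toxicity "thought to be drug-related will lead to cessation of medications". It acts after an event. So do 10(b) and 10(c).
- 7.6 and 10(e): adherence to the study regimen. Taking a drug that 7.4 allows is not non-adherence.
- 10(g): patients who entered in violation, not drugs started later.
- 10(a): intercurrent illness that prevents further treatment. It can apply before a bleed but names no drug.
- 10(f): "General or specific changes in the patient's condition that render the patient unacceptable for further treatment in the judgment of the investigator". This is discretionary and names no drug.

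None carries the bars forward. Items 10(a) and 10(f) let an investigator act but do not require it.

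**2. Would such use be seen?** Under footnote 6 of the Section 6 schedule, salicylate sampling ends at Cycle 5. The run-in is 4 cycles and the randomised stage is Cycles 5-10, so Cycles 6-10 (5 of 6) have no assay. No metformin level is scheduled. Section 13.2 names concomitant medications among its baseline form examples and not among its treatment form examples. Both lists are illustrative, and 13.1 defers to a data capture plan that is not among the documents. On-study capture is therefore not specified, which is different from being ruled out.

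**3. Reproduce the planned size.** Inputs from 16.3: progression 40% against 80%, alpha 0.05, power 80%. The plan names neither test nor sidedness; two-sided is assumed here. The pooled rate is 0.60.

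- Uncorrected: n = [1.960 × √(2 × 0.60 × 0.40) + 0.842 × √(0.40 × 0.60 + 0.80 × 0.20)]² / 0.40² = (1.358 + 0.532)² / 0.16 = 22.3, so 23 per arm.
- With continuity correction: (22.33 / 4) × [1 + √(1 + 4 / (22.33 × 0.40))]² = 27.1, so 28 per arm, the planned figure.

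At 28 per arm, power is 81.6% (continuity-corrected), 82.3% (Fisher exact) or 88.5% (uncorrected z). The sample size is not in error.

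**4. Illustrate dilution.** The documents give no rate of on-study use, so each share and fraction below is an assumption.

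Placebo rate = 0.80 − share of users × fraction of effect gained × 0.40

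| Assumed use in placebo arm | Placebo rate | Fisher power | Uncorrected z power |
|---|---|---|---|
| None | 80% | 82.3% | 88.5% |
| 5%, half effect | 0.80 − 0.05 × 0.5 × 0.40 = 79% | 79.6% | 86.5% |
| 10%, half effect | 0.80 − 0.10 × 0.5 × 0.40 = 78% | 76.8% | 84.4% |
| 20%, half effect | 0.80 − 0.20 × 0.5 × 0.40 = 76% | 70.7% | 79.6% |
| 20%, full effect | 0.80 − 0.20 × 1 × 0.40 = 72% | 57.5% | 68.4% |

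The 5-10% rows represent 1.4 to 2.8 of 28 placebo patients. The entry bars remove established users, so only new starters count, and the lower shares are the more relevant ones.

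**5. Test a blanket stop rule.** Suppose 10% of each arm medically needs one of the two drugs, one drug gives half the effect, and study drug must then stop.

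- Placebo arm: 80% − 2 points = 78%, since the patient still takes the needed drug.
- Active arm: 40% + 0.10 × 0.5 × 40 points = 42%, since the patient loses the other study drug.
- Fisher power: 72.0%, against 76.8% for 40% versus 78% with study drug continued.

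For medically required aspirin or metformin, a mandatory stop lowers power.

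**The case against.** The strongest reply is that the harm is assumed. Established users cannot enter, only about ten cycles remain in which to start, and at 5% use with half effect the Fisher loss is under 3 points. That stands: the power table should not carry the weight of this point.

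Four stronger readings are tempting, and the documents support none of them.

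- A reader might infer that one or two contaminated patients sink the trial, because Fisher power starts only just above 80%. The closeness comes from the rounding of n. The full-effect scenarios need one patient to start both drugs, or one drug to deliver the whole effect, although the trial's premise is synergy between the two.
- A reader might infer that an investigator must wait for a bleed. Sections 10(a) and 10(f) allow earlier action. What is missing is a requirement.
- A reader might infer that on-study use cannot be counted. The 13.2 lists are non-exhaustive, the 4-weekly visits could bring use to light, and the data capture plan and consent pages cannot be seen.
- A reader might infer that study drug should stop whenever any barred drug is needed, citing 7.7. That section covers emergency unblinding only. A stop for aspirin or metformin leaves placebo dilution in place, can weaken the active arm, and may move the patient to PSA every 12-16 weeks (Section 6, footnote 7), which blurs the 6-cycle endpoint.

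None of this closes the gap in the text: 7.4 is an express permission, and no other section qualifies it for non-cancer use.

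**Conclusion.** The point holds as a gap in the protocol's on-study rules and should be fixed. As written, discretionary open-label aspirin or metformin in the placebo arm is allowed without a deviation, as is warfarin or a platelet inhibitor on top of blinded study aspirin. Only general investigator discretion stands against either. That conclusion follows from the text and rests on no assumed rate.

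The statistical effect is probably modest and cannot be sized from the documents. At an assumed 5-10% of placebo patients gaining half the effect (two-sided 0.05, 28 per arm), Fisher power falls from 82% to about 80-77%; on the uncorrected z-test it stays above 84%. The case for change rests on the safety gap and the unprotected control arm.

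**What to change.** Amend 7.4 to keep the general permission but except, in both the run-in and randomised stages:

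- discretionary non-study aspirin and non-study metformin;
- chronic NSAIDs;
- warfarin or platelet inhibitors;
- drugs with a clinically significant interaction with metformin or aspirin;
- the therapies already barred by 7.1 and 7.5.

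Add two rules for medical need:

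- **Anticoagulant or platelet inhibitor required:** stop study drug on safety grounds, keep PSA 4-weekly to the end of the 6 randomised cycles, and continue follow-up under 4.6.
- **Aspirin or metformin required:** leave continuation of study drug to the investigator under 10(a) or 10(f), and keep the patient in the analysis as randomised.

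Record on-study use of all these drugs on the treatment eCRF and report it by arm.

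Cost: an amendment needing IRB approval before use (15.5), a small eCRF addition, 4-weekly PSA for some patients off study drug, and a few patients stopping study drug. The sample size does not change.
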